9.3 STATISTICAL ANALYSES

9.3.1 General Approach

Descriptive statistics will be used to summarize baseline characteristics, adverse events and outcomes from the study treatment. For continuous measures, the mean (standard deviation) or median (interquartile range) will be presented. For categorical variables, the frequency and the percentage in each category will be presented.

9.3.2 Analysis of the Primary Endpoints

The primary endpoint (see Section 3) is the proportion of subjects with stable hematologic recovery (2 consecutive readings) without recent blood product transfusion support (in the past 7 days).

Hematologic recovery is defined as:

Hemoglobin ≥ 10 g/dL (or at least ≥ 2 g/dL above baseline) in subjects with posttransplant anemia. In subjects with symptomatic anemia, a hemoglobin increase of at least ≥ 2 g/dL above baseline is required

OR

Platelets $\geq 50 \times 10^9/L$ (or at least $\geq 20 \times 10^9/L$ above baseline) in subjects with posttransplant thrombocytopenia

OR

Both of the above criteria in subjects with posttransplant Evans syndrome

The proportion of people who meet the above response criteria will be estimated using sample proportions, and their inferences including confidence intervals and hypothesis testing will be evaluated using binomial distributions.

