1 PROTOCOL SUMMARY

1.1 SYNOPSIS

Title:	A Phase II Study of Fostamatinib to Treat Post-transplant Immune-mediated Cytopenias
Study Description:	This open label phase II trial is designed to evaluate the efficacy of fostamatinib in the treatment of post-transplant cytopenias as assessed by hematologic improvement in anemia and/or thrombocytopenia following a 12-week treatment course. Patients who respond to the 12-week treatment course on this single arm study are eligible and have the option to enroll on the extended access trial.
Objectives:	
The primary objective is to assess efficacy of fostamatinib for stable hematologic recovery during post-hematopoietic stem cell transplant immune mediated anemia and/or thrombocytopenia.
 
The secondary objective is to assess efficacy of fostamatinib for clinically-relevant outcomes in post-hematopoietic stem cell transplant patients.
 
The exploratory objective is to evaluate changes in serologic markers that may be associated with cytopenias while on treatment to identify key elements for fostamatinib response.

Endpoints:	
Primary endpoints:
 
The proportion of subjects with hematologic recovery that is stable, defined as improvement documented in 2 consecutive available readings at least 2 weeks apart, without recent blood product transfusion support in the past 7 days.
 
Hematologic recovery is defined as:
 
 • Hemoglobin ≥ 10 g/dL (or at least ≥ 2 g/dL above baseline) in subjects enrolled with posttransplant anemia. In subjects with symptomatic anemia, a hemoglobin increase of at least ≥ 2 g/dL above baseline is required 
OR
 
 • Platelets $\geq 50 \times 10^9/L$ (or at least $\geq 20 \times 10^9/L$ above baseline) in subjects enrolled with posttransplant thrombocytopenia 
OR
 
 • Both of the above criteria in subjects with posttransplant Evans syndrome 
Secondary endpoints:
 
 1. Proportion of subjects who achieve objective hematologic recovery within the 12-week treatment course defined as:

Abbreviated Title: Fostamatinib for post-transplant cytopenias

Version Date: 11/28/2023

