	
 • Hemoglobin ≥ 9 g/dL (or at least ≥ 1 g/dL above baseline) in subjects enrolled with anemia or at least ≥ 1 g/dL above baseline in subjects with symptomatic anemia 
OR
 
 • Platelets $\geq 30 \times 10^9/L$ (or at least $\geq 10 \times 10^9/L$ above baseline) in subjects enrolled with thrombocytopenia 
OR
 
 • Either of the above criteria in subjects with Evans syndrome 
 2. Average weekly requirement of transfused blood component or growth factor requirement (total units of PRBC or Platelets/week, total dose of growth factor/week) by week 12, compared to the week prior to the start of the study drug. 3. Change in corticosteroid dose over time, measured by median daily weight-based prednisone-equivalent corticosteroid dose in a week, from week 1 to week 12 4. Change in other immunosuppressant dose over time, measured by median daily dose of the immunosuppressant in a week, from week 1 to week 12 5. Number of patients who achieved $\geq 50\%$ steroid dose reduction by week 12 compared to week 1 6. Incidence and severity of cGVHD according to 2014 NIH Consensus Criteria, at baseline before the initiation of treatment, and at week 12 
Exploratory endpoints:
 
 1. Absolute percentage change in B cell chimerism pre-treatment, vs weeks 4 and 12. 2. cPRA change in the preformed HLA antibodies before and after treatment in subjects with thrombocytopenia or Evans syndrome 3. Percent MFI change of preformed HLA antibodies before and after treatment. This applies for antibodies with an MFI $>1,000$. 4. Anti-RBC alloantibody titer change in patients with hemolytic anemia before and after treatment 5. Assessment of serial cytokines pre-treatment and weeks 4 and 12. Cytokines include CRP, IL-1, IL-2, IL-6, IFNγ, TNFα, EPO and TPO 6. Immunoglobulin level changes pre-treatment, and weeks 4 and 12. 7. Absolute reticulocyte count, lactate dehydrogenase, haptoglobin changes pre-treatment, and at each biweekly study visit, in patients with anemia or Evans syndrome 8. Change in the weekly rate and severity of bleeding according to the total score of the ITP-Bleeding Scale (IBLS), from week -1 (one week before the start of the study drug) to week 12, in subjects with thrombocytopenia or Evans syndrome

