1.3 SCHEDULE OF ACTIVITIES (SOA)

Study Week ^k	-1	0	2 ^d	4 ^d	6 ^d	8 ^d	10 ^d	12 ^d	14 ^{e,f} (end of study safety visit)
Informed Consent	X ^b	X ^b							
Inclusion/exclusion	X ^b	X ^b							
Pregnancy Test	X ^b	X ^b		X		X		X	
HIV, HBV, HCV testing	X ^{b,j}	X ^{b,j}							
Medical History	X ^b	X ^b							
Medical assessment ^a	X	X	X	X	X	X	X	X	X
Physical Exam	X ^b	X ^b							
Follow up and labs ^{c,d} : CBC, BMP, LFTs, LDH, absolute reticulocyte count, haptoglobin, stool occult blood, urinalysis	X ^b	X ^b	X	X	X	X	X	X	X
Study drug (fostamatinib) administration ^g		X	X	X	X	X	X		
B-cell chimerism and Cytokines ^h		X ^b		X		X		X	
IBLS [1] ⁱ	X ^b	X ^b	X	X	X	X	X	X	
cPRA, MFI, immunoglobulin level, RBC antibody		X		X		X		X	

- a) Vital signs, transfusion support evaluation, concomitant medication review and steroids taper assessment
- b) Can be done within 7 days before or at time of enrollment
- c) Follow up visits will be completed as outpatient in-person visits at the NIH Clinical Center, or via telehealth/telephone if patients are unable to travel for any reason (except for weeks 4 and 12 where patients are required to return to the NIH Clinical Center). Labs can be completed locally, and results will be provided to the research team.
- d) Can be performed +/- 4 days from scheduled visit.
- e) Outpatient visit can be +/- 3 days from scheduled visit.
- f) Patients who rolled over to 000760-H will not need to return for week 14 visit, they will transition all study follow up to 000760-H. The patients who do not roll over will complete their week 14 safety visit on 000758-H.

Abbreviated Title: Fostamatinib for post-transplant cytopenias

Version Date: 11/28/2023

- g) Study drug will be mailed from Rigel or the clinical center pharmacy and be distributed to the research subjects from the pharmacy directly to the research subjects. The pill count will be reviewed every 2 weeks at the medical assessment visit.
- h) Including CRP, IL-1, IL-2, IL-6, IFN γ , TNF α , EPO and TPO
- i) See Appendix B
- j) Within 6 months

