5.1 INCLUSION CRITERIA

- Ages 18-75 years inclusive
- Ability to comprehend the investigational nature of the study and provide informed consent
- Female patients of reproductive potential agree to avoid pregnancy through abstinence or the use of two forms of highly effective birth control during and for 1 month after the last study treatment and agree not to donate eggs during this time
- Male patients of reproductive potential agree to avoid pregnancy of a partner through abstinence or the use of two forms of highly effective birth control during and for 1 month after the last study treatment and agree not to donate sperm during this time.
- Diagnosis of an immune mediated cytopenia (anemia and/or thrombocytopenia)[‡] in a patient that either:
 - Failed or relapsed after at least one line of therapy including steroids, IVIG, TPO mimetics, rituximab, azathioprine, cyclophosphamide, cyclosporine, tacrolimus, danazol, vincristine, ESA or splenectomy
 - Or remains transfusion dependent (≥ 1 transfusion(s)/2 weeks)
 - Or is steroid dependent*
- Subjects are ≥ 60 days post-allogeneic transplant with:
 - Thrombocytopenia, defined as average platelets count $< 30 \times 10^9/L$ for 3 consecutive available readings at least 2 weeks apart, after other cell lines have engrafted, with no counts $> 40 \times 10^9/L$ unless from rescue transfusions. Subjects failed at least one line of therapy outlined above with a clinical diagnosis of immune mediated thrombocytopenia.

- Anemia, transfusion dependent, or defined as hemoglobin ≤ 9 g/dL for 3 consecutive available readings at least 2 weeks apart, after other cell lines have engrafted OR if hemoglobin 9-10 g/dL, subject must have symptomatic anemia or ongoing treatment for immune hemolytic anemia that have failed at least one line of therapy outlined above. Symptomatic anemia is defined as anemia with fatigue, weakness, shortness of breath, palpitations/fast heartbeat, lightheadedness, and/or chest pain, and these symptoms are attributed to anemia. Laboratory evaluation are recommended but not required for the diagnosis, such as a positive DAT, low haptoglobin $<$ lower limit of normal (LLN), indirect bilirubin $>$ upper limit of normal (ULN), or lactate dehydrogenase (LDH) $>$ ULN.
- Subjects must test negative for HIV, HBV, and HCV by standard serologic tests within the previous six months

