- Subjects on other standard of care therapeutic regimens for GVHD or cytopenias should be on a stable dose of medication (no change $\geq 25\%$) for at least 15 days prior to enrollment.
- Patients with a history of hypertension should be maintained on a stable antihypertensive regimen and with controlled blood pressure (Systolic blood pressure < 140 mmHg and diastolic blood pressure < 90 mmHg) for at least one week prior to enrollment.
- Peripheral blood or bone marrow T-cell chimerism $\geq 50\%$ donor cells
- [‡] Immune mediated anemia in subjects with auto or alloantibodies identified due to ABO or non-ABO mismatch transplant, or thrombocytopenia due to identified HLA/HPA antibody. Other causes of immune mediated cytopenias include clinically diagnosed (with or without serologic confirmation) idiopathic thrombocytopenic purpura or autoimmune hemolytic anemia. Subjects with cytopenias attributable to GVHD will be included. Subjects with idiopathic immune mediated cytopenias can also be included. Subjects with evidence for graft rejection per the investigator's opinion ARE NOT eligible for treatment.

* Steroid dependence is defined as inability to tolerate a corticosteroid taper after demonstrating a response to an initial corticosteroid dose (typically 1-2 mg/kg/day). Patients will meet our definition of steroid dependence if their cytopenias relapse or progress before achieving a 50% decrease in the initial corticosteroid dose and/or are unable to have their steroid dose tapered to a dose of less than 20 mg/day of prednisone.

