6.5 CONCOMITANT THERAPY

For this protocol, a prescription medication is defined as a medication that can be prescribed only by a properly authorized/licensed clinician. Medications to be reported in the CRF are concomitant prescription medications used for the treatment of posttransplant cytopenias.

For patients that are eligible for the study, other therapy received prior to enrollment with any other experimental treatment or off-label use of marketed medications or currently stable dose for 15 days prior to enrollment is not an exclusion criterion of the trial.

Do not report vitamins, herbal supplements, or topical medications. Do not report over-the- counter medicines that the subject reportedly took at home prior to enrollment.

Please refer to section 2.3.1 for drug-drug interactions.

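### Secondary endpoint 1 lacks the transfusion condition that section 3.1 attaches to the same term, and the primary endpoint does not classify other cytopenia therapy started or raised on study

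*Combined protocol and SAP*

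**What the plan says.** **Primary endpoint.** The synopsis and section 4 require "improvement documented in 2 consecutive available readings at least 2 weeks apart, without recent blood product transfusion support in the past 7 days". Section 9.3.2 repeats this in shorter form: "stable hematologic recovery (2 consecutive readings) without recent blood product transfusion support (in the past 7 days". No other co-treatment is mentioned in any of the three places.

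**Other therapy for GVHD or cytopenia.** Section 5.1 requires a stable dose (no change of 25% or more) "for at least 15 days prior to enrollment". Nothing extends this requirement past enrolment. Section 6.5 deals with recording: "Medications to be reported in the CRF are concomitant prescription medications used for the treatment of posttransplant cytopenias". The schedule of activities (section 1.3, note a) has each visit cover "Vital signs, transfusion support evaluation, concomitant medication review and steroids taper assessment". Secondary endpoints 2 to 5 follow transfusion and growth-factor use ("Average weekly requirement of transfused blood component or growth factor requirement"), steroid dose and other immunosuppressant dose.

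**Non-response.** Section 9.1 counts early discontinuation for drug-related toxicity or adverse events, or for disease progression, as non-response. Section 9.2.1 repeats the toxicity part.

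**Secondary endpoint 1.** The synopsis and section 4 define objective hematologic recovery by hemoglobin and platelet thresholds, to be reached within the 12-week course. Section 3.1 uses the same term for entry to the extended access trial and adds that the value must be reached without transfusion support.

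**The concern.** Two outcomes can be counted that the plan probably does not intend.

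The first is in secondary endpoint 1. A transfusion raises the count it replaces, and the margins are small: 1 g/dL or 10 x 10^9/L above baseline. With no transfusion condition, one reading taken shortly after a transfusion can qualify. The plan guards against this elsewhere, with 7 days in the primary endpoint and 72 hours in the section 4 baseline footnote.

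The second is in the primary endpoint. Section 5.1 itself names therapies used for these cytopenias ("at least one line of therapy including steroids, IVIG, TPO mimetics, rituximab, azathioprine, cyclophosphamide, cyclosporine, tacrolimus, danazol, vincristine, ESA or splenectomy"). If one of them is started or raised during the 12 weeks while fostamatinib continues, a later stable recovery is a response as written. There is no control arm to absorb the contribution of the other therapy. Without a rule, any decision about such subjects would be made after outcomes are known, in an open-label trial.

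**Working it through.** **1. Secondary endpoint 1 against section 3.1**

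| | Synopsis and section 4 | Section 3.1 |
|---|---|---|
| Term | objective hematologic recovery | the same |
| Anemia | ≥9 g/dL, or ≥1 g/dL above baseline (rise required if symptomatic) | ≥9 g/dL, or 1 g/dL above baseline |
| Thrombocytopenia | ≥30 x 10^9/L, or ≥10 above baseline | ≥30 x 10^9/L, or 10 above baseline |
| Evans syndrome | either | either |
| Readings needed | any within 12 weeks | at least one within 12 weeks |
| Transfusion | not mentioned | none allowed, window not stated |

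No other text supplies the condition. The 72-hour footnote in section 4 covers baseline values only, and section 9.3.3 adds no transfusion rule. Section 6.6 allows transfusions at the discretion of the PI or local provider beyond its stated triggers, so post-transfusion readings are to be expected.

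**2. Places where a rule for added therapy could sit**

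- Section 5.1: the stability requirement ends at enrolment.
- Section 6.1.2.1: the stated response to persistent cytopenia at week 4 is a fostamatinib dose change. Other therapy is not addressed.
- Section 6.5: recording only, with no effect on response status.
- Sections 7.1 and 7.2: starting another cytopenia therapy is not a listed reason for withdrawal.
- Sections 9.1 and 9.2.1: non-response requires stopping treatment.
- Secondary endpoints 2 to 5: doses are tabulated but not linked to a subject's response.

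Take a hypothetical subject who continues fostamatinib, has a steroid raised after week 4, and has qualifying readings at weeks 8 and 10 with no transfusion in the 7 days before either. The subject falls under none of these rules and counts as a primary response.

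**3. The decision rule**

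Inputs from section 9.1: 11 subjects in stage 1, stop at 1 or fewer responses; 20 in total, reject at 5 or more; null rate 10%, alternative 35%. With b the binomial probability,

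P(reject | p) = Σ (x = 2 to 11) b(11, x, p) × P(Bin(9, p) ≥ 5 − x).

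- p = 0.35: 0.8600, matching the stated 86%.
- p = 0.10: 0.0397, within the stated 0.05.

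The design arithmetic is sound. The next figures show how sensitive any such rule is to its counts. They do not measure this gap.

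- P(stage 1 passed and exactly 5 responses) is 0.0288 at p = 0.10. That is 72.6% of the 0.0397 (from unrounded values), or 2.9% of all trials. At p = 0.35 it is 0.1148 / 0.8600 = 13.3% of rejections. In those trials, reclassifying one of the five responders reverses the result.
- If the 10% were a rate without other therapy changes, and added therapy lifted the counted rate to 12% or 15%, P(reject) would be 7.6% or 15.8%. The documents support neither rate.

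**4. What a stricter count would cost**

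Assume that 35% refers to the endpoint as written and that a share l of responders is reclassified, so p = 0.35 × (1 − l).

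| l | p | P(5 or more of 20, stage 1 passed) |
|---|---|---|
| 0 | 0.35 | 86.0% |
| 5% | 0.3325 | 82.3% |
| 10% | 0.315 | 77.9% |
| 20% | 0.28 | 67.0% |

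**The case against.** A reader might infer that the primary result is biased towards fostamatinib and that type I error is inflated. The documents do not establish either. They give no rate of added therapy and no source for the 10%; if the 10% already allows for changes in other therapy, type I error stays at 4.0%. Steroid tapering works in the opposite direction. Section 5.2 excludes cytopenia responsive to standard care, which makes a response to added therapy less likely. The boundary share in the working would be the same for any source of misclassification.

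It is also tempting to take the eltrombopag results in section 2.1 as the success rate of added therapy. The 36% there is for platelets of at least 30 x 10^9/L, below the primary cut-off of 50, and placebo reached 28%, a difference of 36 − 28 = 8 points. The 21% at 50 x 10^9/L comes without a placebo figure and is not said to meet the two-reading rule.

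A further inference is that the stricter definition ought to be the primary one. Counting every therapy change as failure is one defensible estimand, but not the only one. It can fail true responders when a listed drug is raised for an unrelated reason, and the power cost above is real.

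On secondary endpoint 1, section 3.1 is describing who may enter another trial, and section 9.3.3 plans descriptive statistics with no stated hypothesis test for this endpoint. So the primary conclusion is untouched. The shared term and cut-offs still need to be reconciled.

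What survives is that neither gap is closed anywhere in the plan. Recording doses makes the affected subjects identifiable but does not classify them.

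**Conclusion.** Both gaps are in the text and should be fixed.

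Secondary endpoint 1 conflicts with section 3.1 over the same term. As written it can count a single post-transfusion reading as recovery. This needs no assumption about how often therapy is added.

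The primary endpoint leaves unclassified a subject who starts or raises other cytopenia-active therapy while staying on fostamatinib, and a later stable recovery counts. With one arm and a fixed 10%, the response rate cannot be attributed to fostamatinib alone. The frequency of such cases, the net bias and any type I error inflation cannot be determined from the documents. The 4.0%, 86.0% and 72.6% figures describe the Simon rule, not the size of this problem. The finding calls for an endpoint wording correction and a sensitivity analysis; it does not show that the primary test is invalid.

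**What to change.** These changes concern outcome classification only and leave permitted treatment as it is.

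- **Secondary endpoint 1 (synopsis and section 4).** Add the no-transfusion condition so that it agrees with section 3.1, and state a window, for example the primary endpoint's 7 days.
- **Section 9.3.2.** Keep the primary definition. Pre-specify a sensitivity analysis that counts as non-response any subject who, between first dose and the second qualifying reading, starts a therapy on a fixed list or raises one by 25% or more above its stable dose at enrolment. The list in section 5.1 is a starting point. Report both results. Taking the enrolment dose as reference protects tapers: a drug tapered to half and then raised by a quarter stands at 0.5 × 1.25 = 0.625 of that dose and does not count.
- **Section 6.5.** Record listed drugs given for GVHD as well as for cytopenia. Section 5.1 states "Subjects with cytopenias attributable to GVHD will be included", so the recorded indication will not always separate the two.
- **Optional wording.** State whether a transfusion may fall between the two qualifying readings. At the section 6.6 triggers the low count would normally break the consecutive readings, so this matters mainly for discretionary transfusions or the hemoglobin-above-baseline route.

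The cost is endpoint wording, a fixed drug list, some extra medication recording and programming. Transfusions and medications are already reviewed at each visit. The sensitivity result will be somewhat lower than the primary one and may reclassify some true responders; a carefully chosen list limits this.

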9.3.3 Analysis of the Secondary and Exploratory Endpoint(s)

Secondary and exploratory endpoint(s) are listed in Section 3. The analysis of these endpoint will include the descriptive statistics as describe in the general approach (Section 8.3.1). In addition, time-to-event analysis will be performed using appropriate tools in survival analysis such as Kaplan-Meier estimates and cumulative incidence estimates. Paired analysis and regression analysis may be used to analyze certain continuous variables as appropriate. Graphical tools will be used to display the appropriate estimates.

9.3.4 Interim Analyses and stopping rules

- A. Interim analysis for futility: By the study design, there is a planned interim analysis after 11 subjects have been evaluated for the response for the primary endpoint (see section 9.1) . If ≤ 1 subject achieve a response in the first 11 subjects, the study will stop for futility.
- B. Stopping rule for safety

Abbreviated Title: Fostamatinib for post-transplant cytopenias

Version Date: 11/28/2023

We wish to assure that this procedure has less than 25% treatment related SAE (TRSAE) by 12 weeks. We will use a Bayesian approach by Geller et al. [24]. The stopping boundary is reached if the Bayesian posterior probability that the true probability of TRSAE exceeds 0.25 is at least 90%. We take our prior distribution to be a beta distribution so that our prior clinical opinion is worth 20% of the weight we will place on the new data. This gives prior parameters alpha = 1, beta = 3. We will begin monitoring when 2 subjects are evaluable for TRSAE by 12 weeks. The following table summarizes the threshold numbers for the boundary, which would lead to a recommendation to stop the study due to excess TRSAE.

Number of subjects in the study	Stop if the number of subjects who have developed TRSAE by 12 weeks
3 - 4	3
5 - 7	4
8 - 10	5
11 - 13	6
14 - 16	7
17 - 20	8

We investigated the performance of the above stopping rule by a simulation study. In each simulation run, we generated a study with 20 independent Bernoulli trials; each had a probability p for having TRSAE by 12 weeks, and compared the TRSAE outcomes with the above stopping boundary to determine whether the study was stopped. We repeated the simulation 100,000 times and computed the proportion of stopped studies using the above stopping rule. The following table summarizes the performance of the stopping rule under a number of scenarios for TRSAE probability p :

Probability of TRSAE = p	0.1	0.2	0.25	0.3	0.4	0.5
Proportion of Stopped Studies	1%	8%	19%	33%	67%	90%
Average number of subjects	19.9	19.1	18.1	16.7	13.1	9.4
Average number TRSAEs	2	3.8	4.5	5	5.2	4.7

These simulation results suggest that our stopping rule has a low probability stopping a study when the proportion of TRSAE events is below 25%, and the probability of stopping a study is high when the true proportion of TRSAE events exceeds 25%. There, we believe that our Bayesian stopping rule for TRSAE has satisfactory statistical properties.

C. Stopping rule for secondary graft failure

In this study, we would not enroll patients with evidence of graft failure (sections 5.2). Therefore, in this study any graft failure that occurs would be secondary graft failure, which is a known complication of allogeneic stem cell transplantation. Secondary graft failure rates vary in incidence according to the type of transplant, but in general would not be expected to occur in more than 10% of patients [25, 26]. Secondary graft failure is defined as initial blood or marrow donor myeloid chimerism $\geq 5\%$ declining to $< 5\%$ on subsequent measurements. If chimerism assays are technically not possible in the setting of declining blood count in a subject with prior neutrophil recovery and the absolute neutrophil count is sustained at $< 500/\text{mm}^3$, in the absence of other causes, this will be counted as secondary graft failure.

We wish to assure that the rate of secondary graft failure of this study is no more than 10%. We will use a Bayesian approach by Geller et al. [24]. The stopping boundary is reached if the Bayesian posterior probability that the true probability of secondary graft failure exceeds 0.10 is at least 90%. We take our

Abbreviated Title: Fostamatinib for post-transplant cytopenias

Version Date: 11/28/2023

prior distribution to be a beta distribution so that our prior clinical opinion is worth 20% of the weight we will place on the new data. This gives prior parameters alpha = 0.4, beta = 3.6. The following table summarizes the threshold numbers for the boundary, which would lead to a recommendation to stop the study due to excess graft failure.

Number of subjects in the study	Stop if the number of subjects who have developed graft failure
2 - 4	2
5 - 11	3
12 - 17	4
18 - 20	5

We investigated the performance of the above stopping rule by a simulation study. In each simulation run, we generated a study with 20 independent Bernoulli trials; each had a probability p for having graft failure, and compared the graft failure outcomes with the above stopping boundary to determine whether the study was stopped. We repeated the simulation 100,000 times and computed the proportion of stopped studies using the above stopping rule. The following table summarizes the performance of the stopping rule under a number of scenarios for secondary graft failure probability p :

Probability of secondary graft failure = p	0.05	0.10	0.15	0.2	0.25	0.3
Proportion of Stopped Studies	3%	14%	34%	55%	73%	86%
Average number of subjects	19.6	18.4	16.3	13.9	11.5	9.4
Average number graft failures	1	1.8	2.4	2.8	2.9	2.8

These simulation results suggest that our stopping rule has a low probability stopping a study when the proportion of secondary graft failure events is below 10%, and the probability of stopping a study is high when the true proportion of secondary graft failure events exceeds 10%. There, we believe that our Bayesian stopping rule for secondary graft failures has satisfactory statistical properties.

